5. INVESTIGATIONAL PRODUCT

5.1 Manufacturing and Storage

The investigational product as well as placebo product to be used in this study were both manufactured under GMP conditions by an FDA-approved manufacturing facility. Both products should be stored in a cool, dry place at a maximum temperature of 85°F and 70% relative humidity.

5.2 Labeling and Coding

The humic acid and placebo investigational products will be labeled according to the requirements of ICH-GCP guidelines as well as applicable local regulatory guidelines. Investigational products will be randomized and coded by the sponsor. Each investigator will be provided with a randomization list indicating the order of randomization. Each subject will be assigned a randomization code according to the order of the randomization list. The investigator will be provided with sealed envelopes for each randomization code. These envelopes are to remain sealed except in the event of an emergency. In the event that it is necessary to unblind a subject's treatment, the envelope labeled with the subject's randomization code will be opened. Notification of unblinding must be reported to the study sponsor within 24 hours.

Sample Label

Randomization Code: *****	Protocol No.: 10HFHL
Humic Acid Lot No. 072604 or Placebo	
Expiry date: December 2016	
Investigational Natural Health Product	
To be used under the supervision of a qualified investigator.	
Sponsor & Manufacturer:	Laub Biochemicals Corporation
	[name]
For investigational use only. Keep out of reach of children. Store at room temperature.	
Contains: 60 tablets	
Investigator Name: _____	Phone: _____
Subject No.: _____	Subject Initials: _____
Date dispensed: _____	Date returned: _____

5.3 Humic Acid

The active ingredient in the humic acid investigational product is humic acid, 250 mg/tablet. The remaining (inactive) ingredients are: dextrose, sucrose fatty acid ester, silicon dioxide USP/FCC, and sodium starch glycolate USP.

5.4 Placebo

The ingredients in the placebo investigational product are: cantab dextrose, sucrose fatty acid ester, microcrystalline cellulose, and sodium starch glycolate USP.

5.5 Directions

The study product will be supplied in the form of tablets. Subjects will be instructed to take 2 tablets, 3 times daily (TID), preferably with meals. Subjects will be instructed to begin taking the study product on the day following their randomization visit (Treatment Day 1). If a subject

A Pilot Study to Investigate the Effects of Humic Acid on Flu Symptoms

Protocol 10HFHL

misses a dose, they make take it as soon as they remember that day. A subject should not take more than 3 doses in a single day. Subjects will be instructed to return all original packaging and unused tablets at the next study visit. Subjects will also be instructed to record their use of the study product in the subject treatment diary.

5.6 Unblinding

Unblinding should not occur except in the case of emergency situations. In the event that a serious adverse event occurs, for which the identity of the investigational product administered is necessary to manage the patient's condition, the treatment emergency code for that patient may be broken and the investigational product identified. The sponsor must be notified of any unblinding within 24 hours. Details of patients who are unblinded during the study will be included in the Final Report.

6. STUDY ASSESSMENTS

See Appendix 1 for the Schedule of Assessments and procedures.

6.1 Visit 1 – Screen / Baseline

At screening, a Subject Information and Consent Form will be given to each potential subject. The subject will read the information carefully and will be given the opportunity to seek more information if needed. The subject will also be provided with the option of taking the consent form home to review prior to making his or her decision. If agreeable, the subject will sign the consent form and receive a duplicate. Once consent has been obtained, the screening visit will proceed. Each subject will be assigned a screening number at the screening visit. After the subject has signed the informed consent, the screening number will be assigned sequentially and entered in the Screening and Enrollment Log. Screening numbers will be allocated in the chronological order of the subject's signing the informed consent.

Visit 1 shall include:

- review of medical history and concomitant therapies
- vitals signs (heart rate, blood pressure, temperature)
- physical examination (excluding breast, rectal/vaginal examination)
- self-administered questionnaires (symptoms and VAS)
- urine pregnancy test for women of childbearing potential
- a review of inclusion/exclusion criteria
- laboratory tests (hematology, chemistry, and immunological markers)

Eligible subjects will be randomized to humic acid or placebo via the Randomization Schedule provided to the Investigator on the same day.

Subject randomization numbers are to be allocated in the order listed on the Randomization Schedule.

After all visit assessments are performed, subjects will be dispensed the study product.

A Pilot Study to Investigate the Effects of Humic Acid on Flu Symptoms

Protocol 10HFHL

Subjects will receive one of the following treatment regimens:

- humic acid as 2 tablets TID for a total of 6 tablets daily for 14 days
- placebo as 2 tablets TID for a total of 6 tablets daily for 14 days

Subjects will be instructed in detail by site personnel about the dosing regimen. The first dose of study product is to be taken the day after Visit 1 (treatment day 1).

Paper diaries and electronic thermometers will be provided to the subjects. Diaries will be used by subjects to record daily symptom scores, daily oral temperature, investigational product use, concomitant therapy use including treatments taken for symptoms, and changes in health status including adverse effects.

Subjects will be allowed to use concomitant therapies for the treatment of symptoms (i.e., antipyretics, expectorants, throat lozenges). Subjects will be asked to refrain from taking acetaminophen, aspirin, ibuprofen or NSAID within 4 hours prior to temperature readings.

The next visit will be scheduled for day 7 (± 2 days).

Subjects will return to the clinic for follow-up at days 7 and 14.

6.2 Visit 2 / Day 7

Subjects will return the clinic on day 7 (± 2 days). Any remaining investigational product and packaging, and diary will be returned and a new supply of product and new diary will be dispensed.

Study visit assessments will include:

- review of subject diary, concomitant therapies and adverse events
- compliance calculation
- vitals signs
- self-administered VAS questionnaire
- laboratory tests (hematology and immunological markers)

The next visit will be scheduled for day 14 (± 2 days).

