6.3 Visit 3 / Day 14 – End of Study

Subjects will return to the clinic on day 14 (± 2 days). Any remaining investigational product and packaging, and diary will be returned.

Study visit assessments will include:

- review of subject diary, concomitant therapies and adverse events
- compliance calculation
- vitals signs
- self-administered VAS questionnaire
- laboratory tests (hematology, chemistry and immunological markers)

A Pilot Study to Investigate the Effects of Humic Acid on Flu Symptoms

Protocol 10HFHL

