6.5 Laboratory Analysis

Blood samples will be drawn at each study visit as indicated in the Schedule of Assessments.

Protection of subject confidentiality will extend to all data generated from the assaying of these samples. The samples will be alphanumerically coded and the persons performing the analysis will not be aware of the subject's identity.

Whole blood will be collected into EDTA tubes for CBC (includes WBC differential) and T lymphocyte counts (CD4+, CD8+). Serum will be generated from blood collected into SST tubes for electrolytes (Na, K, Cl), glucose, creatinine, AST, ALT, GGT, bilirubin, TNF α , and IL-8.

The urine pregnancy test will be performed at the clinic site.

7. Safety Instructions and Guidance

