12. APPENDICES

Appendix 1. Schedule of Assessments

Procedures/assessments	Visit 1	Visit 2	Visit 3
	Screen/Baseline		End of Study
	Week 0	Week 1	Week 2
	Day 0	Day 7 ± 2	Day 14 ± 2
Informed consent	X		
Review inclusion/exclusion criteria	X		
Review medical history	X		
Review concomitant therapies	X	X	X
Vital Signs (Heart rate, blood pressure, temperature)	X	X	X
Urine pregnancy test as required	X		
Physical exam	X		
Laboratory Tests: General Chemistry electrolytes (Na, K, Cl), creatinine, AST, ALT, GGT, bilirubin	X		X
Laboratory Tests: Hematology CBC, T lymphocyte counts	X	X	X
Laboratory Tests: Cytokines TNF α , IL-8	X	X	X
Symptoms questionnaire	X		
VAS (self-administered)	X	X	X
Dispense investigational product	X	X	
Dispense thermometer	X		
Dispense diary ¹	X	X	
Daily symptoms scores recorded ¹	X	X	X
Daily oral temperature recorded ¹	X	X	X
Return investigational product		X	X
Return/review subject diary		X	X
Compliance calculated		X	X
Review adverse events		X	X

1. Subject is to record daily symptom scores and daily oral temperature in the diary. Investigational product use, concomitant therapy use (including treatments taken for flu symptoms), and changes in health status (including adverse effects) are also to be recorded in the diary.

A Pilot Study to Investigate the Effects of Humic Acid on Flu Symptoms

Protocol 10HFHL

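### No scheduled post-dose liver or kidney result is available while dosing can still be interrupted, although Visit 2 already draws serum and re-dispenses product

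*Protocol*

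**What the plan says.** - **Visit 1 (Section 6.1).** Laboratory tests include chemistry, and product is dispensed after the visit assessments. "The first dose of study product is to be taken the day after Visit 1 (treatment day 1"), so this sample is pre-dose.
- **Visit 2, Day 7 ± 2 (Section 6.2).** Laboratory work is "laboratory tests (hematology and immunological markers"), with no chemistry. The first supply comes back and "a new supply of product and new diary will be dispensed". The other checks are vital signs, compliance, the VAS and "review of subject diary, concomitant therapies and adverse events".
- **Visit 3, Day 14 ± 2 (Section 6.3).** Laboratory work is "laboratory tests (hematology, chemistry and immunological markers"). Remaining product is returned and none is dispensed.
- **Appendix 1.** The row "Laboratory Tests: General Chemistry electrolytes (Na, K, Cl), creatinine, AST, ALT, GGT, bilirubin" is marked at Visits 1 and 3 only. The row beginning "Laboratory Tests: Cytokines TNF" is marked at all three visits.
- **Section 6.5.** "Serum will be generated from blood collected into SST tubes for electrolytes (Na, K, Cl), glucose, creatinine, AST, ALT, GGT, bilirubin", and also for TNF alpha and IL-8. Chemistry and cytokines therefore use the same tube type.
- **Section 7.1.4.** An abnormal result is clinically significant if, among other conditions, it leads to product being interrupted or stopped. AST or ALT above 2 x ULN is given as a criterion for recording an adverse event.
- **Section 7.2.2.** Clinically significant unexplained abnormalities are repeated and followed.
- **Section 4.4.** Discontinuation is at the investigator's discretion. End-of-study evaluations at withdrawal are done only where possible.
- **Section 8.2.** The safety analysis covers all randomized subjects and includes general chemistry.

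**The concern.** A safety test protects the subject only if its result arrives while something can still be changed. Here the only scheduled post-dose chemistry is taken when the remaining product is handed back. A rise in AST, ALT, bilirubin or creatinine during the first week, with no symptom, would not be seen on schedule until there was nothing left to withhold. Vital signs, hematology and questioning about adverse events do not measure liver or kidney function.

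The second stake is data. Chemistry is a named safety parameter, yet a completer contributes one scheduled post-dose value, and a subject lost after Visit 2 may contribute none. That subject would still have post-dose hematology and cytokines. For safety background, the protocol's introduction cites only acute studies in live animals, so on-treatment chemistry would be useful information from a 14-day course.

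**Working it through.** **Inputs.** 2 tablets three times daily for 14 days (Section 6.1); first dose on the day after Visit 1 (Sections 5.5 and 6.1); Visit 2 on Day 5 to 9 and Visit 3 on Day 12 to 16 (Sections 6.2 and 6.3, Appendix 1). Laboratory turnaround is not in the protocol, so 0 to 3 days is assumed.

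**Course length.** 2 x 3 = 6 tablets a day, which reproduces the daily total in Section 6.1. Over 14 days this is 3 x 14 = 42 doses, or 84 tablets.

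**Doses taken by a visit on Day d.** This is 3(d − 1) if none has been taken that day and 3d if all three have, with a ceiling of 42.

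**Exposure at the first scheduled post-dose chemistry (Visit 3).**
- Day 12: 33 to 36 doses.
- Day 14: 39 to 42 doses.
- Day 16: 42 doses.

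In every case none can follow, because product is returned.

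**Doses from the Visit 2 supply, and doses still to come once a Visit 2 result is known.** Full compliance and dosing to Day 14 are assumed. With a turnaround of t days, the result arrives at the end of Day d + t, leaving 42 − 3(d + t).

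| Visit 2 on | Taken by Visit 2 | Left of 42 | Left, t = 0 | t = 1 | t = 2 | t = 3 |
|---|---|---|---|---|---|---|
| Day 5 | 12–15 | 27–30 | 27 | 24 | 21 | 18 |
| Day 7 | 18–21 | 21–24 | 21 | 18 | 15 | 12 |
| Day 9 | 24–27 | 15–18 | 15 | 12 | 9 | 6 |

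- Dispensed at Visit 2: 15 to 30 doses (15/42 = 36%, 30/42 = 71%).
- Could be withheld at 1 to 2 days: 9 to 24 doses (9/42 = 21%, 24/42 = 57%).
- Could be withheld at 3 days: 6 to 18 doses (6/42 = 14%, 18/42 = 43%).

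**If Visit 3 is early.** On Day 12 the total taken is 33 to 36, so 42 − 36 = 6 to 42 − 33 = 9 doses drop out of these counts. With Visit 2 on Day 9 after all three doses (27 taken) and Visit 3 on Day 12 before any (33 taken), only 33 − 27 = 6 doses follow Visit 2. In that pairing a 2-day turnaround gives a result at the end of Day 11, after 33 doses, so 0 to 3 remain.

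**Scheduled post-dose chemistry values per subject.**
- Completer: 1 now, 2 with chemistry at Visit 2.
- Lost after Visit 2: 0 now unless the withdrawal evaluations are done, 1 with chemistry at Visit 2.

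**The case against.** The strongest reply is that chemistry at baseline and end of treatment is a design choice for a 14-day course. The relevant sections agree with one another, and no section calls for mid-course chemistry. Safeguards exist: Visit 2 reviews adverse events, vital signs and hematology; Section 7.1.4 covers results from tests outside the protocol, so unscheduled chemistry is possible; Visit 1 results that come back in the first days of dosing can be acted on; and the investigator may withdraw a subject at any time. All of this stands and keeps the point small. It does not close the gap, because none of these checks would detect a silent rise that begins after dosing starts.

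A reader might infer more than the protocol supports:

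- **That 15 to 30 doses could be saved.** That is the number supplied at Visit 2. The number that could be withheld depends on an unstated turnaround and on the visit dates, and can fall to zero.
- **That a 2 x ULN stopping rule is being defeated.** Section 7.1.4 uses that figure to record adverse events, not to hold product. A compulsory hold at that level would be a new and debatable rule. These subjects are acutely ill and may take analgesics, so rises unrelated to product are foreseeable, and holds would reduce exposure in arms of 20.
- **That no repeat-dose safety data exist.** The introduction is a background summary. It shows only that the protocol cites acute animal studies.
- **That one tube is certainly enough.** Section 6.5 gives the tube type but no volumes.

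**Conclusion.** The point holds as a minor weakness in safety monitoring. As scheduled, no post-dose AST, ALT, GGT, bilirubin or creatinine result can lead to interruption of product, and a subject who leaves after Visit 2 may have no post-dose chemistry. How many subjects that would be is unknown, because the protocol gives no dropout rate.

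The gain from a Visit 2 panel is a second post-dose value for completers, at least one for everyone who attends Visit 2, and in most visit pairings a result in time to withhold some doses: about 9 to 24 of 42 if results take 1 to 2 days and dosing runs to Day 14. Those counts assume full compliance; only the turnaround is invented. The documents do not support calling the schedule contradictory, and they report no liver or kidney signal. The efficacy analysis and the sample size are not affected.

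**What to change.** Add AST, ALT, GGT, bilirubin and creatinine to the Visit 2 laboratory tests in Section 6.2, and mark them at Visit 2 in Appendix 1. Run them on the SST serum drawn there for TNF alpha and IL-8, or on one more tube at the same draw if volume is short. State that the investigator reviews the results on receipt and acts under the existing discretion in Section 4.4 and the repeat-and-follow provision in Section 7.2.2. Visit 3 would then also provide a scheduled repeat of an abnormal Visit 2 value. No compulsory hold threshold is needed.

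The cost is at most 40 extra panels (one per subject), with no new visit and no new needle stick, plus occasional follow-up of rises due to influenza or analgesics. The change is the same in both arms, so the blind is unaffected.

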6.3 Visit 3 / Day 14 – End of Study

Subjects will return to the clinic on day 14 (± 2 days). Any remaining investigational product and packaging, and diary will be returned.

Study visit assessments will include:

- review of subject diary, concomitant therapies and adverse events
- compliance calculation
- vitals signs
- self-administered VAS questionnaire
- laboratory tests (hematology, chemistry and immunological markers)

A Pilot Study to Investigate the Effects of Humic Acid on Flu Symptoms

Protocol 10HFHL

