2. STUDY OBJECTIVES

The primary objective of this study is to assess the efficacy of humic acid on flu symptoms as assessed by the alleviation of symptoms after 7 and 14 days of treatment in adults with influenza A or B. This will be determined by the use of a daily diary to assess the following symptoms during the trial on a 4-point scale (0=absent, 1=mild, 2=moderate, 3=severe):

[figure not shown]
- cough
- fever
- runny nose
- stuffy nose
- aches and pains
- headache
- chills
- sneezing
- ear aches
- fatigue

Additional endpoints will include:

- Visual analog scale (VAS) 0-100 mm, for ability to perform usual activities
- Doses of concomitant therapies for symptom treatment
- Immunological markers (WBC differential, CD4+, CD8+, TNF α , IL-8)

A Pilot Study to Investigate the Effects of Humic Acid on Flu Symptoms
Protocol 10HFHL

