3. STUDY DESIGN

This is a multi-center, randomized, double-blind, placebo-controlled, parallel-group efficacy pilot study.

The study will consist of a single 14-day treatment period. Screening and randomization will occur on the same day.

The planned sample size for the study is 40 subjects, with 20 subjects randomized equally to each of the two study arms. The subjects will be recruited over the flu season.

Subjects will be randomized to one of the two treatment groups: Humic Acid or Placebo.

In order to evaluate primary and secondary endpoints, study assessments will be conducted at baseline, Day 7 and Day 14.

The study will be conducted at two sites in the US.

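### Minor: Visit 3 ends dosing and the diary, yet its window lets it fall on Day 12 or 13, short of the 14-day course; Day 14 (0 to +2 days) would cure most of this cheaply

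*Protocol*

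**What the plan says.** Protocol Section 3 fixes the course: "The study will consist of a single 14-day treatment period". It also names the assessment days: "study assessments will be conducted at baseline, Day 7 and Day 14". Section 6.1 gives the regimen for the active arm as "humic acid as 2 tablets TID for a total of 6 tablets daily for 14 days", with the same tablet count for placebo. Sections 5.5 and 6.1 place the first dose on the day after Visit 1, which is treatment Day 1.

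Section 2 states the primary objective as "alleviation of symptoms after 7 and 14 days of treatment", to be determined from a daily diary.

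Section 6.2 schedules the last visit: "The next visit will be scheduled for day 14 (± 2 days"). Section 6.3 then says: "Subjects will return to the clinic on day 14 (± 2 days). Any remaining investigational product and packaging, and diary will be returned". Appendix 1 repeats the window. It dispenses product and diary at Visits 1 and 2 only, and labels Visit 3 as the end of the study. Section 8.2 rules out imputing symptom scores and bases the average score on whatever days are available.

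**The concern.** A tolerance of two days either side is ordinary for a clinic visit. The difficulty is that this visit also ends dosing and the diary. At Visit 2 the same tolerance does no harm, because a new supply and a new diary are handed out. At Visit 3 nothing follows, and no sentence tells an early attender to carry on to Day 14. A site that takes the product back on Day 12, as Section 6.3 directs, cannot also deliver the 14 days of Sections 3 and 6.1.

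At stake are a somewhat shorter exposure in early attenders, the lack of a Day 14 diary entry in them, and averages taken over unequal numbers of days. An analysis plan can equalise the span of days. It cannot restore doses not taken or entries never made.

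**Working it through.** **Inputs.** Visit 1 is Day 0 and the first dose is on Day 1 (Section 6.1, Appendix 1). The dose is 6 tablets daily for 14 days (Section 6.1). Strength, from Section 5.3: "The active ingredient in the humic acid investigational product is humic acid, 250 mg/tablet". Visit 3 may fall on Days 12 to 16 (Section 6.3).

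**Planned course.** 6 × 14 = 84 tablets; 84 × 250 mg = 21 g of humic acid in the active arm.

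**Course by day of Visit 3.** For a visit on Day d, the completed days are min(d − 1, 14) if the visit day is not counted and min(d, 14) if it is. Tablets are 6 times that.

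| Visit 3 on | Treatment and diary days | Tablets of 84 | Short by | Day 14 entry |
|---|---|---|---|---|
| Day 12 | 11–12 | 66–72 | 12–18 | no |
| Day 13 | 12–13 | 72–78 | 6–12 | no |
| Day 14 | 13–14 | 78–84 | 0–6 | only if made before or at the visit |
| Day 15 or 16 | 14 | 84 | 0 | yes |

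An early attender therefore misses 6 to 18 tablets: 6/84 = 7.1% to 18/84 = 21.4%, or 1.5 g to 4.5 g in the active arm.

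**Across the trial.** The protocol does not give the share of early visits. Assume that 5% to 40% of 40 completers come early, split evenly between Days 12 and 13. Visits are aimed at Day 14, so the upper end is unlikely. The planned total is 40 × 84 = 3,360 tablets.

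- 5% is 2 subjects, one on each day: 12 + 6 = 18 to 18 + 12 = 30 tablets lost, 0.5% to 0.9%.
- 40% is 16 subjects, eight on each day: 8 × 12 + 8 × 6 = 144 to 8 × 18 + 8 × 12 = 240 tablets lost, 4.3% to 7.1%.

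So 2 to 16 subjects would have no Day 14 entry.

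**Noise in the average score.** Take the worst case for the average: symptoms are gone by Day 12, so that the symptom total is the same whatever the span. Cut diaries at Day 14 and assume that the visit-day entry is made. The average is then multiplied by 14/n with n = min(d, 14), giving 1.167, 1.077, 1, 1 and 1 for Days 12 to 16. If visit day is independent of symptoms, the relative increase in variance is CV_f² × (1 + CV_s²) / CV_s². Here CV_f is the coefficient of variation of the factor and CV_s that between subjects, assumed to be 0.50, so the multiplier is 1.25/0.25 = 5.

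- Visits spread evenly over Days 12 to 16: CV_f = 0.063, and 0.063² × 5 = 2.0%.
- 2.5% of visits on each of Days 12, 13, 15 and 16, the rest on Day 14: CV_f = 0.028, and 0.028² × 5 = 0.4%.
- A common span of days for all subjects: no added noise.

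**The case against.** The strongest reply is that nothing of consequence is lost. Section 8.1 says that this is a pilot without a formal sample size calculation, and the only analysis rule in the protocol averages the available days, so an early attender still has a value to analyse. Section 2 speaks of 14 days of treatment but does not define a single-day score. This stands: the missing Day 14 entry matters only if a Day 14 score is analysed, and the averaging span may properly be left to the analysis plan.

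It is also fair to say that the harms cannot all be at their worst together. If symptoms have gone by Day 12, the noise figure is at its highest, but the missing entry would be about zero and the omitted tablets would have no symptom left to treat. In the other direction, leaving out the visit-day entry would raise the even-spread figure to about 4.5%, but Appendix 1 marks daily scores at Visit 3.

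A third reply is that the window is only a scheduling tolerance and that Section 6.1 already has subjects told to dose for 14 days. That leaves two instructions in conflict once the product is returned, and the protocol does not say which prevails.

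A reader might go further and infer a bias between the arms, a loss of power, or a primary objective that cannot be assessed. The documents do not support this. The trial is randomized and double-blind with one window for both arms, and nothing in the text ties the visit date to treatment or recovery. No power is stated that could be lost. The Day 7 assessment is untouched, and an average can be formed for everyone with diary data.

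**Conclusion.** The point holds as a minor improvement. The protocol fixes a 14-day course and a 14-day objective, then permits a final visit that cuts both short by one to three days, counting the visit day or not. The day and tablet counts follow from the text alone. The trial-level loss rests on the assumed share of early visits. The noise figure rests on the assumed between-subject variation, the symptom pattern and the spread of visits. It is worth acting on only because the change is cheap and because no later analysis can recover what was not taken or recorded.

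**What to change.** Change the Visit 3 window in Sections 6.2 and 6.3 and in Appendix 1 to Day 14 (0 to +2 days). Have the Day 14 diary entry completed at or before the visit. State that dosing and the analysed diary end at Day 14, which also settles what a Day 15 or 16 attender should do. Section 3 already names Day 14 and needs no change.

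Moving the visit to Days 15 to 16 would complete the course in everyone, but is not advised. Chemistry is drawn only at Visits 1 and 3, so the only post-baseline chemistry, the final immunological markers and the last activity VAS would fall off treatment in every subject, and only two days would be left for the visit. With weekend closure (an assumption), Friday enrolees would have no working day at all.

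**Cost.** The window shrinks from 5 days to 3, which makes an out-of-window or missed visit somewhat more likely, and drop-outs are not replaced. Day 14 always falls on the weekday of Visit 1, which limits this. A Day 14 visit may still miss up to 6 tablets (6/84 = 7.1%). Visits up to two days after the last dose are already permitted.

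**Supply.** The sample label in Section 5.2 reads "Contains: 60 tablets". Assuming one container per dispensing visit, that is enough. With Visit 2 on Day 5, Days 5 to 14 need at most 10 × 6 = 60 tablets; with Visit 2 on Day 9, the first container must cover at most 9 × 6 = 54.
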